12 PFAS contamination of drinking water is widespread with at least six million U.S. residents receiving water 13 having concentrations of PFOA and PFOS (individually or combined) exceeding the EPA's Lifetime Health 14 Advisory of 70 parts per trillion (Kray 2018). Sources of the drinking water contamination include 15 emissions from manufacturing facilities and the use of AFFF at military bases and airports. For example, 16 the Air Force and Navy have identified at least 24 bases with contaminated drinking water in several states 17 including Alaska, California, Colorado, Delaware, Michigan, New Hampshire, New Jersey, New York, Ohio, Pennsylvania, Virginia and Washington (Kray 2018). At these bases, PFAS chemicals in the AFFF likely 18 19 leached into the soil and ground water and migrated to drinking water supply wells.

20 An example of a community drinking water supply contaminated via the use of AFFF at a military base is 21 the Pease International Tradeport, Portsmouth, New Hampshire. In 2014, a drinking water supply well 22 had measured PFOS, PFOA and PFHxS concentrations of 2.5 μ g/L, 0.35 μ g/L, and 0.96 μ g/L, respectively. 23 The source of the contamination was use of AFFF at the former Pease Air Force Base. In 2015, NH DHHS 24 established a Pease biomonitoring program for PFAS. The program obtained blood specimens for PFAS 25 analyses from 1,578 persons (NH DHHS 2016, Daly 2018). The results from the blood-testing program indicated that the exposed population had serum levels of PFOS and PFHxS that were about two to three 26 27 times higher than the U.S. population based on data from NHANES 2013-4 and from other epidemiological 28 studies in the U.S. In analyses conducted by NH DHHS (Daly 2018), geometric mean PFHxS serum levels 29 were higher for persons who drank \geq 4 cups of water per day compared to those who drank <4 cups per 30 day (4.76 µg/L versus 3.77 µg/L). NH DHHS measured 8 to 14 PFAS congeners at 3 analytical laboratories.

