Behavior Rating Inventory of Executive Function [®] – Preschool Version (BRIEF [®] -P)	Executive Function - Preschool	4-5	Parent about Child	10 minutes

1

For each child, the recipient will also review and abstract school records, including special education records, to identify learning problems and behavioral problems (Attachment 18b). If the parent reports that the child has a developmental disability (e.g., ADHD, autism, or a learning disability), then the recipient shall obtain and abstract the special education records for the child including the individualized education program (IEP), the IEP evaluation report ("Full Individual Evaluation" or "FIE"), and if available, the Independent Educational Evaluation.

8 3.6.5.2 Adults

9 Each adult participant will complete a questionnaire requesting demographic information, residential 10 history, water consumption habits, occupational history, medical history and reproductive history (Attachment 16). In particular, the questionnaire will ask if the participant ever had kidney disease, liver 11 12 disease, cardiovascular disease, hypertension, high cholesterol, thyroid disease, diabetes, autoimmune 13 diseases, osteoporosis, osteoarthritis, pregnancy-induced hypertension, infertility, and endometriosis. 14 For each reported disease or condition, the questionnaire will ask about the date of diagnosis, the medical 15 provider who made the diagnosis, and the medications used for treatment the questionnaire will ask the 16 participant about conditions that might affect PFAS serum levels such as date of menopause, menstrual

- 1 cycle information, blood transfusions, and blood donations. The study will attempt to confirm diseases
- 2 and conditions reported in the questionnaire by medical records review (Attachments 17&17a).

3 3.6.6 Exit Procedures

At the end of the data collection, study coordinators or staff will review recorded items in the participant's
Appointment Tracking Form for completeness (Attachment 9).

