The residual blood specimens will be stored with the study-generated ID only. ATSDR will keep a separate dataset that can link the study ID with the participant's name. If participants change their minds later about letting their blood used for additional analyses, they can contact ATSDR and we will remove their specimens. We do not plan to provide participants the results of these future tests, but we may contact them if we learn something that is important.

27 3.8.7 Future Exploratory Analyses

- 1 CDC IRB approval will be sought for this additional research either as a protocol amendment or under a
- 2 new research protocol prior to undertaking this plan.

3 **3.9 Exposure Estimation**

4 The study will use the fasting serum PFAS measurements obtained from study participants to estimate 5 exposures. In addition, the study will estimate each participant's cumulative PFAS serum level, using:

- PFAS serum measurements obtained in the study,
- Historical reconstruction of PFAS concentrations in the drinking water consumed by the
 participant,
- 9 Questionnaire data on the participant's consumption of PFAS-contaminated drinking water and
 10 factors that might affect PFAS serum levels,

• Age-, sex-, and calendar year-specific "background" PFAS serum levels from NHANES, and

12 • Physiologically based pharmacokinetic (PBPK) models.

13 If previous PFAS serum measurements are available for some of the participants (e.g., from a 14 biomonitoring program), then these results will be used to validate the modeled historical PFAS serum 15 estimates.

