 the source via ground water, then the recipient should seek information on the extent of the
 contamination plume from the state environmental agency, EPA, and/or the industrial facility.

If the contaminated drinking water is from a municipal system, then the characteristics of the distribution system will be obtained from the water purveyor. If supply wells are used, then the recipient will request historical and current information on these wells including monthly or daily production logs and dates of operation. If a surface water source is used or if water is purchased from another purveyor, then the recipient will request information about this source.

10 The recipient will also request the results of all relevant PFAS sampling: in the surface water near the 11 drinking water intakes, in the distribution system, in the supply wells and nearby monitoring wells, in 12 purchased water from other water purveyors, and in the private wells in the study area.

13

14 **3.10 Statistical Analyses**

15 ATSDR staff will perform statistical analyses with the participation of the recipients using SAS, R and STATA 16 on the combined multi-site study dataset. ATSDR staff may also use SPSS for data management. ATSDR 17 staff will calculate descriptive statistics (including means, geometric means, medians, standard deviations, 18 and percentiles) to identify the presence and distribution of PFAS and effect biomarker analytes. Statistical 19 methods will include multiple linear regression of continuous (untransformed and natural log transformed) effect biomarkers on continuous (untransformed and natural log transformed) PFAS serum 20 21 levels and categorized PFAS serum levels, and logistic regression of categorized effect biomarkers (e.g., 22 hypercholesterolemia) or disease prevalence on continuous (untransformed and natural log transformed) 23 and categorical PFAS serum levels. ATSDR staff will use restricted cubic spline methods (or generalized 24 additive models using cubic regression splines) for linear and logistic regression to obtain flexible, 25 smoothed exposure-response curves. To identify risk factors that may act as confounders for a particular health outcome, the analysis will implement a "10% change in the estimate" rule (Maldonado 1993). 26

Primary analyses will focus on estimated cumulative PFAS serum levels. Supplemental analyses will
evaluate PFAS serum levels in the blood specimens obtained in the study as well as estimated maximum

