and average PFAS serum levels. The primary analyses will evaluate each PFAS chemical separately; sum

of PFAS measures may also be considered. Statistical analyses using prevalent cases in a cohort design 1 2 which takes into consideration the times of diagnosis will also be conducted. ATSDR will explore the use 3 of methods for evaluating multi-pollutant mixtures, such as the hierarchical Bayesian model, to analyze 4 the effects of exposures to the PFAS mixtures. ATSDR will use quantitative methods to assess the impact 5 of possible selection bias and possible confounding due to unmeasured risk factors (Lash 2009). There 6 are several caveats and recommendations in conducting analyses of mixtures to determine the optimal 7 method that avoids amplifying bias due to confounding (Weisskopf et al 2018). For the bias analyses, ATSDR will identify "negative control" diseases with no known association with PFAS exposures (Lipsitch 8 9 2010). ATSDR conducted a literature search to identify these negative control diseases and included them 10 in the questionnaire.

ATSDR will interpret the findings from this study based on the magnitude of the effect estimates (e.g., the linear regression coefficient for continuous outcomes or the odds ratio for categorical outcomes) of the exposure-response relationship, consistency with findings from other studies, and the possible sources of bias (Rothman 2014). The analyses will construct confidence intervals to indicate the level of precision (or uncertainty) in the effect estimates.

The studies will use statistical significance testing to interpret findings but will not use it as a sole factor in determining scientific and public health significance (Rothman et al. 2008, 2010; Stang et al. 2010). A finding that fails to achieve statistical significance can still provide evidence for a causal association, and a finding that achieves statistical significance can lack any such significance (Porta 2014).

20 4. RESULTS REPORTING

21 4.1 Notification of Individual Results

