Section B: Residential History and Drinking Water Exposures

This next set of questions is about the child and the child's birth mother. If you are not her, we can follow up after this interview with a quick phone call to complete the questionnaire.

B1. What is the main source of tap water in your home?

____Public water system

____Private well

____Other: specify _____

____Don't know

_____Refused to answer

B2. On average, how many 8 oz. cups of tap water or beverages prepared with tap water does your child currently drink per day at home?

____ cups

____Doesn't drink tap water

____Don't know

____Refused to answer

Note: 1 cup = 8 oz.; 2 cups = 1 pint (16 oz.); 4 cups = 1 quart (32 oz.); 16 cups = 1 Gallon (128 oz.

B3. On average, how many 8 oz. cups of tap water or beverages prepared with tap water do you currently drink per day at home?

____ cups

____Doesn't drink tap water

____Don't know

Refused to answer

Note: 1 cup = 8 oz.; 2 cups = 1 pint (16 oz.); 4 cups = 1 quart (32 oz.); 16 cups = 1 Gallon (128 oz.

B4. What was your previous address?

Street	Apt	
City	State	Zip Code:

B5. When did you move into your previous address? Month____ Year_____

B6. What was the main source of tap water at that address?

____Public water system

____Private well

____Other: specify _____

____Don't know

_____Refused to answer

B7. On average, how many 8 oz. cups of tap water or beverages prepared with tap water did your child drink per day when living at your previous address?

____ cups

_Don't drink tap water

Don't know

____Refused to answer

____Your child did not live at this address

Note: 1 cup = 8 oz.; 2 cups = 1 pint (16 oz.); 4 cups = 1 quart (32 oz.); 16 cups = 1 Gallon (128 oz.

B8. Have you or your child lived at any other address since January 2000?

___Yes

__No → go to Section C

____Don't know \rightarrow go to Section C

____Refused to answer \rightarrow go to Section C

B9. Please fill out the table below for these other residences where you or your child lived since January 2000.

Street Address, City, State	Did your	Your child's average	Move in	Main source of
	child live	consumption of tap	(mm/yy)	tap water at
	at this	water per day (# cups)		this address
	address?	at this address		(public water
				system or
				private well?)

Note: 1 cup = 8 oz.; 2 cups = 1 pint (16 oz.); 4 cups = 1 quart (32 oz.); 16 cups = 1 Gallon (128 oz.

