Section F: Child's Medical History

F1. Have you ever been told by a doctor or other health care provider that your child has or had any of the following medical conditions? Fill out the table below. Circle appropriate response and ask the respondent to specify as directed.

м	edical condition		If yes, what year was your child diagnosed?
-		Yes (Please specify)	year
a. Ca	ancer?	No Don't know	
b. All	lergies?	Yes (Please specify) No Don't know	year
c. At	copic dermatitis/eczema?	Yes (Please specify) No Don't know	year
d. As	sthma?	Yes No Don't know	year
e. Ch (rł	nronic stuffy/runny nose hinitis/sinusitis)?	Yes No Don't know	year
f. Hi	gh cholesterol?	Yes No Don't know	year
g. Th	nyroid disease?	Yes (Please specify) No Don't know	year
h. De	elayed puberty?	Yes (Please specify) No Don't know	year
i. Ot	besity?	Yes No Don't know	year
j. Lu	ipus	Yes No Don't know	year
k. Ce	eliac disease	Yes No Don't know	year
l. Cr	ohn's disease	Yes No Don't know	year
m. Di	abetes	Yes, Type 1 Yes, Type 2 Yes, Type unknown No Don't know	year

	Medical condition		If yes, what year was your child diagnosed?
n.	Scleroderma	Yes No Don't know	year
0.	Attention deficit hyperactivity disorder (ADHD) or attention deficit disorder (ADD)?	Yes No → go to p Don't know → go to p	year
p.	How is your child treated for ADHD or ADD?		year
q.	Other learning or behavioral problems?	Yes (Please specify) No \rightarrow go to Question F2. Don't know \rightarrow go to Question F2.	year
r.	How is your child treated for their learning or behavioral problems?		

F2. What age was your child last vaccinated for:

Diphtheria, Tetanus, Pertussis ("DTaP")	age	Don't know	never was vaccinated
"Tdap" booster Tetanus, Diptheria, Pertussis	age	Don't know	never was vaccinated
Measles, Mumps, Rubella ("MMR")	age	Don't know	never was vaccinated
Tetanus shot (for a puncture wound or cut)	age	Don't know	never was vaccinated

FOR GIRLS ONLY

F3. Has your daughter ever used an oral contraceptive ("birth control pill")?

- ____Yes
- ___No \rightarrow go to Question F5
- ____Don't know \rightarrow go to Question F5
- ____Refused to answer \rightarrow go to Question F5

F4. When did your daughter last use an oral contraceptive ("birth control pill")?

___ Month/Year

F5. At what age did your daughter begin menstruation (have her first period)?

___Age

- ____Has not yet begun to menstruate \rightarrow go to Section G
- ____Don't know
- F6. Does your daughter's period occur regularly (every month)?

____Yes

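### The primary exposure takes in tap-water intake reported in the same questionnaire as the diseases, and no planned analysis could tell a differential-reporting bias apart from reverse causation

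*Protocol*

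**What the plan says.** Section 3.10 states: "Primary analyses will focus on estimated cumulative PFAS serum levels". Analyses of serum measured at the study visit are supplemental.

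Section 3.9 lists the inputs to the cumulative estimate. The first is "PFAS serum measurements obtained in the study". The others are reconstructed water concentrations, questionnaire data on each participant's "consumption of PFAS-contaminated drinking water and" other factors that affect serum, NHANES background levels, and a PBPK model. No weights are given for own serum against reported intake.

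Intake and disease share an instrument. In section 3.6.5.2 the adult questionnaire covers residential "history, water consumption habits, occupational history, medical history and reproductive history". In the long child form (Attachment 15), Section B asks "how many 8 oz. cups of tap water or beverages prepared with tap water does your child currently drink per day at home" and repeats the question for earlier addresses back to 2000. Section F of the same form asks "Have you ever been told by a doctor or other health care provider that your child has or had any of" a list of conditions.

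On bias, section 3.10 plans quantitative methods for the impact "of possible selection bias and possible confounding due to unmeasured risk factors", and adds negative-control diseases. Section 5 discusses reverse causation and survivor bias, and mentions accurate exposure assessment in general terms. Differential reporting of intake is not named.

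**The concern.** Modelled serum is offered in section 5 as a way round reverse causation, because measured serum can be changed by the outcome, with kidney function as the example. Part of the modelled value, however, is a recalled quantity. Reconstructed water concentrations do not depend on how a respondent remembers cups per day; intake does. The invitation letters (Attachments 5a and 5b) tell recruits that the study asks whether PFAS in drinking water might affect health.

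Medical-record review under section 3.6.5.2 checks the disease, not the intake answer of a true case. If cases report more water than non-cases with the same real intake, their modelled exposure rises and the odds ratio moves away from 1 with no real effect. If they report less, it moves the other way. The outcomes at stake are those the respondent knows about, such as osteoarthritis, thyroid, cardiovascular and autoimmune disease and endometriosis.

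**Working it through.** **1. The plan's own figure.** Table 2 gives 978 per stratum for osteoarthritis at an odds ratio of 1.55 and prevalence 7.6%, two-sided alpha 0.05, power 80%. With p1 = 0.076, p2 = 0.1131, and the pooled-variance two-proportion formula without continuity correction, n = 977. The figure reproduces, so nothing in Table 2 is in dispute here.

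**2. Model for the bias.** True odds ratio 1. Log modelled exposure is normal with SD s, and cases are shifted by δ = a × ln(1 + r × w), where:

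- r is the proportional over-report by cases: 0.10 or 0.20 (assumed).
- w is the share of serum due to water. Section 2.2 puts Pease PFOS and PFHxS at about two to three times the U.S. level, so w = 1 − 1/2 = 0.50 to 1 − 1/3 = 0.67. No such ratio is given for PFOA.
- a is the part of the shift left after calibration to own serum: 1 for none removed, 0.5 if half is removed (assumed).
- s is 0.6 to 1.2 (assumed); prevalence 10%.

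The top and bottom quarters of a normal exposure have means about 2.54 SDs apart (2 × 1.27). A shift δ in cases corresponds to a log odds ratio of δ/s² per log unit. The false Q4 versus Q1 odds ratio is therefore about exp(2.54 × δ/s), and exact quartile calculation agrees.

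| r | w | δ, a = 1 | OR, s = 1.2 to 0.6 | δ, a = 0.5 | OR, s = 1.2 to 0.6 |
|---|---|---|---|---|---|
| 10% | 0.50 | 0.049 | 1.11 to 1.23 | 0.024 | 1.05 to 1.11 |
| 10% | 0.67 | 0.065 | 1.15 to 1.32 | 0.032 | 1.07 to 1.15 |
| 20% | 0.50 | 0.095 | 1.22 to 1.50 | 0.048 | 1.11 to 1.22 |
| 20% | 0.67 | 0.126 | 1.31 to 1.71 | 0.063 | 1.14 to 1.31 |

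**3. Benchmark.** For diseases reported in the questionnaire, Table 2 uses odds ratios of 1.42 to 1.77 (osteoarthritis), 1.58 to 1.89 (thyroid disease), 2.01 (cardiovascular) and 3.05 (ulcerative colitis). Lower values in that table, such as 1.25 for elevated ALT, are laboratory outcomes and are not a fair comparison.

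**4. False-positive rate.** For osteoarthritis with continuous log exposure, z = (δ/s) × √(N p (1 − p)), and √(6,000 × 0.076 × 0.924) = 20.5. With s = 1.0, w = 0.67 and r = 20%:

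- a = 1: z = 0.126 × 20.5 = 2.58, rejection probability about 73%.
- a = 0.5: z = 0.063 × 20.5 = 1.29, rejection probability about 25%.

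The nominal rate is 5%.

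**5. How firm is the serum anchor?** Section 3.2.1 gives half-lives of about 3 years (PFOA, PFOS) and 5 years (PFHxS), with 5 to 8 years from another source, and admits people last exposed up to 15 years ago. The fraction of the water-derived excess left after 15 years is 2^(−15/3) = 3%, 2^(−15/5) = 13% or 2^(−15/8) = 27%. Own serum therefore says least about people whose exposure ended long ago.

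**6. Does reported intake carry signal?** Section 2.2 gives "geometric mean PFHxS serum levels" of 4.76 µg/L for 4 or more cups a day against 3.77 µg/L for fewer, a ratio of 1.26, and a marginal effect of 36.4% at age 19 or under. Reported intake is informative, so dropping it from the primary exposure would lose real variation.

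**The case against.** The strongest reply is that only a protocol is shown and a sensitivity analysis is ordinary SAP content. That stands in part: nothing here is a wrong statement or a contradiction. But the protocol itself fixes the primary exposure, lists its inputs and names the biases to be quantified, so the gap can be seen at this level.

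A reader might infer that the primary disease analyses are biased and will produce false associations. The documents do not support that. They give no evidence that over-reporting occurs, nor its direction or size. All participants come from exposed communities, so awareness is not confined to cases.

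A reader might also infer that nothing planned bears on the problem. That is wrong too. Negative-control diseases asked about in the questionnaire could show the same spurious association. Measured serum is free of reported intake. Section 3.9 also plans comparison with study serum and, where available, validation against earlier serum.

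What remains is attribution. A negative control can signal recall or confounding but does not correct the primary estimate. If measured and modelled serum disagree, the cause could be recall in one or reverse causation in the other.

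**Conclusion.** The concern holds as a conditional risk for questionnaire-reported diseases. Under the assumed 10 to 20% over-reporting by cases, the false quartile odds ratio is about 1.1 to 1.7 with no serum anchoring and about 1.05 to 1.3 with half anchoring. Only the upper part of the unanchored range reaches the planned 1.42 to 1.89, and no 10% scenario does. The over-report, the SD and the anchoring fraction are assumptions, and the water share rests on Pease PFOS and PFHxS alone. The structural point does not depend on them: no planned exposure is free of both individual recall and own serum. The change is worth making, with medium confidence in the size of the problem.

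**What to change.** In sections 3.9 and 3.10, for questionnaire-reported diseases:

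- Add a sensitivity exposure: cumulative serum from residence history and reconstructed water concentrations, with age- and sex-standard intake, using neither individual reported intake nor calibration to own serum.
- Report it beside the primary and measured-serum estimates.
- Add differential reporting of intake to the biases assessed quantitatively in section 3.10.
- State that an association seen only with reported intake may be due to recall, allowing for the attenuation that standard intake will cause. Requiring both versions to agree would be too strict, because it would penalise true but attenuated associations.

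A regression of measured serum on an intake-by-disease interaction should not be used as a direct test. With log intake and a disease main effect, uniform proportional over-reporting goes into the main effect; in simulation the interaction rejected only about 4 to 6% of the time. If a check is wanted, regress measured log serum on residence-based modelled serum, log reported intake and a disease main effect, and read it cautiously because disease may itself alter serum PFAS.

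The cost is one extra run of the exposure model, with no new data, and some loss of true intake variation in the sensitivity version.
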